2.3.2. Potential Benefits

There are no specific anticipated potential benefits to subjects for participating in this study, although subjects may benefit from the close follow-up and detailed medical care associated with study participation. It is not known whether treatment with mexiletine will be helpful for ALS subjects. It is possible that results from the study may yield benefits to future ALS patients.

3.0. STUDY OBJECTIVES

3.1. Primary

The primary study objective is to determine whether treatment with mexiletine at doses of 300 mg or 600 mg/day suppresses cortical hyperexcitability in sporadic ALS patients relative to placebo, and, thus, may be able to slow progression in ALS. The change in RMT, estimated from single pulse TMS measurements made before treatment, after 4 weeks of treatment, and then again after a 4 week washout, will be used as the primary pharmacodynamic marker of cortical hyperexcitability.

3.2. Secondary

Secondary pharmacodynamics outcome measures will include effects on motor evoked potential (MEP) amplitude (as a % of CMAP) and cortical silent period (CSP) measured by single pulse TMS, and SICI measured by dual pulse TMS, as additional pharmacodynamic markers of cortical hyperexcitability, prior to and following treatment with mexiletine or placebo. Additionally, as a pharmacodynamic marker of peripheral motor nerve axonal hyperexcitability, threshold tracking nerve conduction studies (TTNCS) will be performed to assess strength duration time constant and recovery cycle analysis. Safety and tolerability and determination of mexiletine concentrations in blood at the time of each of the four TMS studies will also be assessed. Additionally, the effect on frequency and severity of muscle cramps and fasciculations will be assessed using a daily muscle cramps/fasciculations diary from the Baseline Visit through the Week 8 Visit and using an assessment form at the Baseline Visit. ALS Functional Rating Scale-Revised (ALSFRS-R) and slow vital capacity (SVC) will be obtained at Screening, Pre-Dose Baseline, Week 4, and Week 8 or the Final Safety Visit, if applicable as exploratory outcomes.

4.0. STUDY DESIGN

4.1. Overall Study Design and Plan

During the enrollment period, approximately 90 sporadic ALS (sALS) patients will be screened at approximately 9 Northeast ALS Consortium (NEALS) centers in the US. Approximately 60 eligible sALS subjects will be randomly assigned in a 1:1:1 ratio to oral mexiletine 300 mg/day, 600 mg/day or matching placebo. After randomization, subjects will undergo the Baseline Visit and take their first dose of study drug in clinic at that visit. All visit windows are consecutive calendar days and are calculated from the day the participant has their Baseline Visit (Day 1).

In the phase II study, within three weeks following screening, RMT will be assessed by single pulse TMS prior to initiating study drug (baseline), four weeks after initiating placebo or mexiletine at either 300 mg or 600 mg per day, and then again after a four week washout period. Therefore, there will be a total of four visits (screening, baseline, week 4, and week 8). To ensure tolerance, the medication dose will be escalated over the course of one week. The RMT will serve as a pharmacodynamic marker of the effects on cortical excitability in ALS using this medication. The goal of these studies is to determine if targeting this putative mechanism of motor neuron injury in ALS reduces this excitability (significantly increases the RMT), which may serve as a pathogenic mechanism for the disease, potentially slowing progression in ALS.

Secondary outcome measures will include effects on MEP amplitude % and CSP measured by single pulse TMS, and SICI by dual pulse TMS, as additional pharmacodynamics markers of cortical hyperexcitability and TTNCs as a pharmacodynamic marker of peripheral motor axonal hyperexcitability (and therefore a potential marker for the therapeutic effect of mexiletine on muscle cramps and fasciculations), prior to and following treatment with mexiletine or placebo and then again after withdrawal of treatment. Safety and tolerability and determination of mexiletine concentrations in blood at the time of each of the two post-baseline TMS studies will also be assessed. Additionally, the effects on muscle cramps and fasciculations will be determined utilizing an Assessment Form at Baseline, and by employing a daily muscle cramping and fasciculations diary describing both frequency and severity of these symptoms from the Baseline Visit through the Week 8 Visit. Finally, ALSFRS-R, APB testing via HHD, and SVC will be obtained at Screening, Pre-Dose Baseline, Week 4, and Week 8 or the Final Safety Visit, if applicable.

4.2 Informed Consent

At the screening visit, prior to initiation of any study-related procedures, research participants will give their written consent to participate in the study after having been informed about the nature and purpose of the study, participation/termination conditions, and risks and benefits.

The appropriate ICF will be presented to the research participant and reviewed by the Site Investigator or study staff designee. The original signed and dated consent form will be maintained in the participant's research file. One copy of the signed informed consent form will be given to the research participant and one will remain in the research participant's medical/research record per site standards. The Site Investigator will determine study eligibility as determined by the inclusion and exclusion criteria.

Informed consent can only be obtained by the Site Investigator for the purposes of this research study.

4.3. Study Centers

This study will be conducted at approximately 9 NEALS centers in the US selected because of their excellent record of recruitment, compliance with study protocols and regulations, clinical research expertise and resources.

4.4. Study Duration

There will be an enrollment period of approximately 40 weeks (10 months) during which time subjects will be screened and randomized. Subjects will receive study medication for a total of 4 weeks (1 month).

4.5. Protocol Adherence

Each Site Investigator must adhere to the protocol detailed in this document and agree that any changes to the protocol must be approved by the Coordination Center or their representative prior to seeking approval from the site IRB. Each Site Investigator will be responsible for enrolling only those study subjects who have met protocol eligibility criteria.

5.0. STUDY ENROLLEMENT AND WITHDRAWAL

5.1. Number of Study Subjects

Approximately 60 subjects will be enrolled and equally randomized 1:1:1 to receive 300 mg/day oral mexiletine or 600 mg/day oral mexiletine or placebo.

5.2. Inclusion and Exclusion Criteria

5.2.1. Inclusion Criteria

Volunteers will be eligible if they meet the following criteria:

1. Sporadic ALS diagnosed as possible, laboratory-supported probable, probable, or definite ALS as defined by revised El Escorial criteria.
2. Age 18 years or older.
3. Symptom onset of weakness or spasticity due to ALS \leq 60 months prior to Screening Visit.
4. Slow vital capacity (SVC) measure \geq 50% of predicted for gender, height, and age at the screening visit.
5. Must be able to swallow capsules throughout the course of the study, according to Site Investigator judgment.
6. Capable of providing informed consent and following trial procedures.
7. For TMS: a resting motor threshold, defined as 50% of pulses eliciting a motor evoked potential (MEP) of amplitude \geq 50 μ V.
8. For TTNCS: Median CMAP \geq 1.5 mV.
9. Subjects must not have taken riluzole for at least 30 days or be on a stable dose of riluzole for at least 30 days prior to the Screening Visit and continue on the stable dose throughout the course of the study (riluzole-naïve subjects are permitted in the study).
10. Subjects must not have taken medication for muscle cramping such as cyclobenzaprine, baclofen, carisoprodol, or methacarbamol, for at least 30 days prior to screening or be on a stable dose for at least 60 days prior to screening.
11. Geographic accessibility to the site.
12. Women must not become pregnant for the duration of the study and must be willing to use two contraceptive therapies and have a negative pregnancy test throughout the course of the study.
13. Use of medications known to affect the neurophysiology measures in the study must be scheduled, not as needed (pro re nata, PRN). A subject must have been on a fixed dose for 30 days prior to the Screening Visit, and there must be no reason to believe that a subsequent change would be necessary during the course of the study. These medications include: benzodiazepines, muscle relaxants, tricyclic antidepressants, selective serotonin reuptake inhibitors, non-selective serotonin reuptake inhibitors, hypnotics (including anti-histamines) and anti-cholinergics.

5.2.2. Exclusion Criteria

Volunteers who meet any of the following criteria are not eligible:

1. Invasive ventilator dependence, such as tracheostomy.
2. Creatinine level greater than 1.5 mg/dL at screening.

3. SGOT (AST) / SGPT (ALT) greater than 3 times the upper limit of normal at screening.
4. History of known sensitivity or intolerance to mexiletine or lidocaine.
5. Any history of either substance abuse within the past year, unstable psychiatric disease, cognitive impairment, or dementia.
6. Clinically significant conduction abnormalities on electrocardiogram or a known history of cardiac arrhythmia.
7. Known history of epilepsy.
8. Known history of congestive heart failure (CHF) or history of myocardial infarction within the past 24 months.
9. Use of mexiletine for 30 days prior to Screening Visit.
10. Exposure to any other experimental agent (off-label use or investigational) including high dose creatine (>10 grams a day) within 30 days prior to Screening Visit.
11. Metal in the head and neck region, cardiac pacemaker or brain stimulator, cochlear implants, implanted infusion device or personal history of epilepsy.
12. Use of amiodarone, flecainide, duloxetine, tizanidine, or clozapine.
13. Pregnant women or women currently breastfeeding.
14. Placement of Diaphragm Pacing System (DPS) device < 60 days prior to Screening Visit.
15. Planned DPS device implantation during study participation.

Riluzole. Subjects taking concomitant riluzole at study entry must be on a stable dose for 30 days prior to the Screening Visit and must continue taking the same dosage throughout the study, unless the Site Investigator determines that riluzole should be discontinued for medical reasons.

Date of ALS Symptom Onset. For the purposes of this study, the date of symptom onset will be defined as the date the subject first had symptoms of their disease, i.e., weakness. To be eligible for this study, the date of symptom onset must be no greater than exactly 60 months prior to the Screening Visit date.

5.3. Re-screening

Participants who are determined ineligible may be re-screened a single time if their ineligibility was due to one of the following time-limited or modifiable criteria: inclusion criterion 2, 8, 9, 10, 11, or 13 or exclusion criterion 9, 10, 12, 13, 14, or 15. Re-screened participants will be issued a new screening identifier that is linked to their original screening identifier.

5.4 Randomization Procedures

A permuted-block randomization schedule, stratified by site and use of riluzole at screening, will be developed by the study statistician with assignments in a 1:1:1 ratio among 300 mg/day oral mexiletine, 600 mg/day oral mexiletine, and placebo. If a randomized subject withdraws from the study prior to initiating study drug, their assignment will be released and re-used.

5.5. Reasons for Withdrawal

A subject will be withdrawn from the study if:

- Any clinical AE, laboratory abnormality, concurrent illness, or other medical condition or situation occurs such that continued participation in the study would not be in the best

interest of the subject. Note, however, that any subject who has initiated treatment should only discontinue study drug and remain on study if the safety concern relates to study drug and not to study procedures.

- The subject no longer meets eligibility criteria at any time prior to initiating study drug or is discovered at anytime to have been enrolled in error.

Subjects are free to withdraw from participation in the study at any time upon request.

5.6. Handling of Withdrawals

The medical monitor should be notified in all instances a subject may choose to discontinue their participation, start a prohibited medication, or wishes to withdraw consent.

A subject may choose to discontinue participation in the study at any time. However, the SI or designee will encourage subjects to continue with follow-up, regardless of their compliance with study drug. If a subject who initiated study drug permanently discontinues study drug, the SI or designee should still encourage subjects to follow the study protocol under the modified intent-to-treat principle (ITT). Subjects unable or unwilling to return for clinic visits should be encouraged to receive follow-up telephone calls per the study visit schedule up to Week 8. These calls will include administration of the ALSFRS-R and review of adverse events and concomitant medications. Loss to follow-up should be prevented whenever possible

Any subject who is on study drug and needs to begin the use of any prohibited medication, must immediately discontinue use of study drug and should not begin use of the prohibited medication before an appropriate wash-out period occurs. Subjects who permanently discontinue study drug should return any unused study drug and complete early study drug discontinuation procedures without any study drug unblinding, if possible. Subjects who must permanently discontinue study drug may continue in the ITT portion of the study, per protocol.

If a subject wishes to withdraw consent, i.e., withdraw his or her participation in future study procedures, the subject will be asked to delay consent withdrawal to allow for a final safety visit and final safety telephone call. The subject will be asked to return to the study site for a final safety visit within 14 days of asking to withdraw consent. The subject will also be asked to have a final telephone call no sooner than 28 days after taking their last dose of study drug to monitor their safety and to permit review of their medical records at the end of the study to document their vital status.

Subjects who discontinue study drug due to an AE will be followed for outcome measures under the ITT protocol as noted above.

5.7. Termination of Study

This study may be prematurely terminated if, in the opinion of the PI or sponsor, there is sufficient reasonable cause. Written notification, documenting the reason for study termination, will be provided to the PI or sponsor by the terminating party.

Circumstances that may warrant termination include, but are not limited to:

- Determination of unexpected, significant, or unacceptable risk to subjects.

- Enrollment is unsatisfactory.
- Insufficient adherence to protocol requirements.
- Data that is not sufficiently complete and/or evaluable.
- Plans to modify, suspend or discontinue the development of the study drug.

If the study is prematurely terminated or suspended, the sponsor will promptly inform the investigators/institutions, of the termination or suspension and the reason(s) for the termination or suspension. The site IRBs will also be informed promptly and provided the reason(s) for the termination or suspension by the sponsor or by the investigator/institution. Study subjects will be called to explain the decision to terminate the trial and asked to return study drug at a final safety visit scheduled to occur within 14 days after last known dose of study drug. If the study was prematurely terminated due to safety concerns, they will be provided with relevant safety information to share with their primary care provider.

[figure not shown]
6.0. TREATMENT OF SUBJECTS

6.1. Treatments

6.1.1. Mexitil

Mexitil (Mexiletine hydrochloride [mexiletine]) is an orally active anti-arrhythmic agent available as 150 mg, 200 mg and 250 mg capsules. One-hundred milligrams (100 mg) of mexiletine is equivalent to 83.31 mg of mexiletine base. It is a white to off-white crystalline powder with slightly bitter taste, freely soluble in water and in alcohol. Mexiletine has a pKa of 9.2.

Chemically, mexiletine 1-methyl-2-(2, 6-xylyloxy) ethylamine hydrochloride has the following structural formula:

Mexitine capsules contain the following excipients: corn starch, NF. The capsule shell contains: FD&C Yellow #6, gelatin and titanium dioxide. The 150 mg capsule also contains D&C Red #28 and FD&C Blue #1. The imprinting ink contains ammonium hydroxide, black iron oxide, D&C Yellow #10, ethyl alcohol, FD&C Blue #1, FD&C Blue #2, FD&C Red #40, isopropyl alcohol, n-butyl alcohol, propylene glycol and shellac.

The mexiletine capsules will be over-encapsulated in #00 Swedish Orange Opaque (4188) capsules and will be overfilled with corn starch, NF.

6.1.2. Placebo

A matched placebo will be used to maintain the dosage-blind. The placebo capsules for this study will match the corresponding mexiletine capsules in size, color, and presentation.

The placebo capsules are #00 Swedish Orange Opaque (4188) capsules and will be overfilled with corn starch, NF.

Administration of matching placebo will be the same as for subjects in the two mexiletine treatment groups.

6.2. Treatments Administered

The three treatment arms include placebo, mexiletine 300 mg/day, and mexiletine 600 mg/day. Mexiletine or the matching placebo will be taken orally as a capsule. Subjects must be able to

swallow oral medication at the Baseline Visit and expected to be able to swallow the capsule throughout the course of the study to be eligible for enrollment. The capsules must not be opened and mixed with food/drink or any gastrostomy feedings. Study drug capsules must be taken with solid food or antacids. It may not be taken with a liquid diet.

Capsules will contain 150 mg of either placebo or mexiletine and will be administered concurrently from two bottles containing 60 capsules each. Study subjects will be titrated up to the appropriate dosage level over the course of 7 days (see Table 5. Study Drug Titration Schedule). After the titration period, the subject will continue at the target dosage level of 2 capsules twice a day until the Week 4 Visit. Mexiletine and placebo will be packaged in kits. Each subject is expected to utilize one kit during study participation. Additional drug kits will be shipped to each site, as needed based on enrollment.

Mexiletine or placebo will be started at the Baseline Visit and continue treatment until the Week 4 Visit. The day that a subject starts treatment with study drug will be designated as Day 1. All subsequent visits must be scheduled from the Baseline Visit, not the date of their last assessment. The first dose of study treatment will be administered in the clinic by authorized site personnel and will be observed in clinic for 1-2 hours post-dose.

6.2.1. Dosage Initiation/Escalation

Given the gastrointestinal (GI) side effects to taking mexiletine, a titration approach was chosen for this study. Mexiletine will be supplied as 150 mg capsules in bottles containing 60 capsules. Study drug kits will contain two bottles labeled 1 and 2. Each participant will start with 1 capsule a day, the first dose taken at the Baseline Visit and the second taken in the am from bottle 1 for 2 days (Day 1 – 2). Subjects will follow the titration schedule illustrated below in Table 5 until the full study dosage level is reached at Day 7. After initial titration, subjects will take 2 capsules of study drug in the morning and in the evening. One capsule will be taken from each bottle labeled with a 1 in the morning and evening until the Week 4 Visit. Each bottle is good for 4 weeks of dosing.

Table 5. Study Drug Titration Schedule

Number of capsules per bottle per day – Bottle 1 and 2

	Day 1-2	Day 3-4	Day 5-6	Day 7
Bottle #1	1 QD	1 BID	1 BID	1 BID
Bottle #2	-	-	1 Q AM	1 BID

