6.4. Study Drug Adjustments, Dosage Reductions and Suspensions

Any dosage adjustment including the reason for and dates of adjustment will be documented in the CRF for each subject requiring this manipulation. The Site Investigator or licensed physician Sub-Investigator has the option of reducing or temporarily stopping the study drug for AEs thought to be related to the study drug or any other reason during the trial (the reason for, and dates of suspension or dose reduction must be documented). If the adverse event is mild or moderate, the dosage may be reduced until the event improves (See Table 6. Study Drug Reduction Schedule). The Site Investigator may then choose to resume the higher dosage or maintain the subject at a reduced dosage. If the event is serious or life threatening, and deemed to be drug related, the study drug should be discontinued immediately. Study subjects may remain off the study drug permanently, until the condition improves or they may resume on a reduced dosage, as advised by the Site Investigator. Subjects may not resume study drug after a suspension that is longer than 10 days. Any resumption of drug after a suspension requires approval from the Medical Monitor. All adverse events will be followed for resolution or 28+5 days after stopping study drug.

Table 6. Study Drug Reduction Schedule: Number of capsules per bottle per day

	Day 1-2 Dose Reduction	Day 3-4 Dose Reduction	Day 5-6 Dose Reduction
Bottle #1	1 BID	1 BID	1 Q AM
Bottle #2	1 Q AM	-	-

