2.6 Treatment Administration

Study drug will be orally self-administered from 2 bottles containing either 150 mg capsules of mexiletine or placebo capsules matched for size, color, and presentation. All participants will take one capsule for bottle #1 at their baseline visit (day 1) and on the morning of day 2, one capsule from bottle #1 BID from day 3 until their week 4 visit, one capsule from bottle #2 on the morning of days 5 and 6, and one capsule from bottle #2 BID from day 7 until their week 4 visit.

In the placebo arm, bottles #1 and #2 will contain placebo capsules, and the dosage of mexiletine will be 0 mg/day throughout their participation. In the 300 mg/day arm, bottle #1 will contain 150 mg capsules of mexiletine and bottle #2 will contain placebo. Dosage of mexiletine will be titrated as follows: 150 mg at their baseline visit, 150 mg on the morning of day 2, and 150 mg BID (300 mg/day) from day 3 until their week 4 visit. In the 600 mg/day arm, bottles #1 and #2 will contain 150 mg capsules of mexiletine. Dosage of mexiletine will be titrated as follows: 150 mg at their baseline visit, 150 mg on the morning of day 2, 150 mg BID (300 mg/day) on days 3 and 4, 300 mg QAM and 150 mg QPM (450 mg/day) on days 5 and 6, and 300 mg BID (600 mg/day) from day 7 until their week 4 visit.

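### Protocol 6.2.1: the maintenance dosing sentence leaves out bottle 2 and, taken at its word, would give both active arms 300 mg/day

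*Protocol*

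**What the plan says.** Protocol section 6.2.1 describes a kit of two bottles, labelled 1 and 2, with 60 capsules in each. Titration follows Table 5 "until the full study dosage level is reached at Day 7", where the table shows one capsule twice daily from both bottles. The text then gives the maintenance dose: "After initial titration, subjects will take 2 capsules of study drug in the morning and in the evening". The next sentence assigns those capsules to bottles: "One capsule will be taken from each bottle labeled with a 1 in the morning and evening until the Week 4 Visit". The paragraph ends: "Each bottle is good for 4 weeks of dosing".

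Four other places bear on the same instruction:

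- Protocol section 6.2 has capsules taken from the two bottles at the same time, and after titration "the subject will continue at the target dosage level of 2 capsules twice a day until the Week 4 Visit".
- SAP section 2.6 has "one capsule from bottle #2 BID from day 7 until their week 4 visit", alongside bottle 1 twice daily from day 3.
- SAP section 2.6 also gives the contents: "In the 600 mg/day arm, bottles #1 and #2 will contain 150 mg capsules of mexiletine". In the 300 mg/day arm bottle 1 is mexiletine and bottle 2 is placebo; in the placebo arm both are placebo.
- Protocol section 6.4 sets out dose reductions in "Table 6. Study Drug Reduction Schedule: Number of capsules per bottle per day". Its Day 3-4 step is bottle 1 twice daily with nothing from bottle 2.

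**The concern.** Only one bottle in the kit carries a 1, so the sentence gives two capsules a day where the sentence before it gives four. It also describes, as the maintenance regimen, a combination that Table 6 lists as a reduced dose.

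This is the only place in the protocol that assigns capsules to bottles after Day 7: Table 5 stops at Day 7, and section 6.2 gives a capsule count without saying how many come from each bottle. SAP 2.6 has the schedule right, but the SAP's opening section makes the SAP authoritative on analysis only and leaves everything else to the protocol. The SAP therefore does not formally correct a dosing sentence.

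Bottle 2 is what makes the 600 mg/day arm different from the 300 mg/day arm. A site or participant who followed the sentence alone would remove the dose contrast for most of the treatment period.

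**Working it through.** **Inputs.** Capsule strength 150 mg (protocol 6.2, SAP 2.6). Daily capsules from Table 5 and SAP 2.6:

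| Days | Bottle 1 | Bottle 2 |
|---|---|---|
| 1-2 | 1 | 0 |
| 3-4 | 2 | 0 |
| 5-6 | 2 | 1 |
| 7 onward | 2 | 2 |

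The Week 4 Visit falls on Day 29 to 32, with the last dose the night before (protocol 8.1.5), so the last dosing day is Day 28 to 31.

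**Reproducing the plan's doses.** Daily dose = 2 × (bottle 1 content) + 2 × (bottle 2 content).

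- Placebo: 0 mg.
- 300 mg/day arm: 2 × 150 + 2 × 0 = 300 mg.
- 600 mg/day arm: 2 × 150 + 2 × 150 = 600 mg.

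Four capsules a day therefore give the stated doses.

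**Capsules scheduled, Days 1-28.**

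- Bottle 1: 2 × 1 + 26 × 2 = 54.
- Bottle 2: 2 × 1 + 1 × 2 + 21 × 2 = 46.
- Total: 100.

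With last dosing on Day 31 the counts are 60 and 52, total 112. Both fit 60-capsule bottles, in line with the statement that each bottle lasts four weeks.

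**The sentence taken at its word.** Titration runs as in Table 5 through Day 7; from Day 8 only bottle 1 is used, one capsule twice daily. Bottle 2 then contributes 2 × 1 + 1 × 2 = 4 capsules in all. The daily dose from Day 8 is 2 × 150 = 300 mg in both active arms.

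| | Through Day 28 | Through Day 31 |
|---|---|---|
| Capsules taken / scheduled | 58 / 100 (58%) | 64 / 112 (57%) |
| 600 mg/day arm, intended | 100 × 150 = 15,000 mg | 112 × 150 = 16,800 mg |
| 600 mg/day arm, as worded | 58 × 150 = 8,700 mg | 64 × 150 = 9,600 mg |
| 300 mg/day arm, either way | 54 × 150 = 8,100 mg | 60 × 150 = 9,000 mg |
| Gap between active arms, intended | 6,900 mg | 7,800 mg |
| Gap between active arms, as worded | 600 mg | 600 mg |

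**A second misreading.** A reader who kept two capsules twice daily but took all of them from bottle 1 from Day 8 would give the 300 mg/day arm 4 × 150 = 600 mg/day. Bottle 1 uses 2 × 1 + 5 × 2 = 12 capsules by Day 7, and the remaining 48 last 48 / 4 = 12 days, so it would be empty on Day 19. That contradicts the four-week bottle life.

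**Would it be noticed?** Protocol 6.7 defines non-compliance as under 80% or over 120% by capsule count, so 58% would be flagged. Bottles come back at the Week 4 Visit or Final Safety Visit, however, normally after dosing has ended. The Week 1 call checks compliance at 7 ± 3 days, and a call made before Day 8 could not show the departure.

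**The case against.** The best reply is that the sentence is incomplete rather than contradictory. The sentence before it fixes the dose at two capsules each time. If one of them comes from bottle 1, the other can only come from bottle 2. The text never says to use bottle 1 alone or to stop bottle 2, and the word *each* suggests that both bottles were in the author's mind. Section 6.2, Table 5 and the four-week bottle life all agree, so the protocol settles the matter without the SAP. On this view the milligram figures describe something only a careless reader would do, and more than one misreading is possible.

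Most of this stands. The intended regimen is recoverable, the figures are conditional, and nothing in the documents shows that the label, the diary or any participant's dosing followed the faulty wording. The Table 6 comparison also depends on reading the sentence in isolation.

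It does not make the sentence right. A dosing instruction that names one bottle where two are meant should not need reconciling with other sections, least of all when the omitted bottle defines the treatment contrast.

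**Conclusion.** The concern holds as a minor wording error in an operative dosing instruction. It is not a flaw in the design, the analysis or the power calculation. As worded, the sentence omits bottle 2 and disagrees with the rest of the plan.

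If it were followed exactly from Day 8, both active arms would take 300 mg/day, and the cumulative gap between them through Day 28 would shrink from 6,900 mg to 600 mg. That size assumes titration as in Table 5, complete adherence to the sentence, and bottle contents as in SAP 2.6. The number of participants affected is unknown and may be zero.

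**What to change.** In section 6.2.1, replace the reference to a bottle labelled with a 1 by a reference to each of bottles 1 and 2, so that one capsule is taken from each of the two bottles, morning and evening, up to the Week 4 Visit. This gives four capsules a day and 0, 300 and 600 mg/day in the three arms, matching the preceding sentence, Table 5, section 6.2 and SAP 2.6. Then check that the kit label and dosing diary give the same instruction; their contents are not in the documents.

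The cost is a one-sentence protocol clarification and a check of two participant-facing items. Design, drug supply and analysis are unchanged.
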